4.2 Study Duration

Recruitment/enrollment for the pilot version of this study began in November 2020 and will continue until July 2021. Recruitment/enrollment for the full version of this study is anticipated to begin in August 2021 and will continue until January 2024. We estimate that up to 40 participants will have completed the pilot version of the study by July 2021, and we estimate that up to 120 participants will have completed the study by August 2024, for a total of 160 participants completing the study. Each participant will be considered “active” within the study for 21 days per the study design.

4.3 Rationale

4.1.1 Rationale for within-subject design

We chose a within-subjects design for several reasons. First, our proposed aims and hypotheses reflect intra-individual change across time. Baseline smoking rate will be established across five days of ad-libitum smoking. Cigarette smoking subsequent to the introduction of IQOS will be compared to each participant's baseline smoking rate (Day 1-5 vs. Day 8-21, see Figure 1). Randomly assigning smokers to continue to smoke their own cigarettes or to switch to IQOS in a between-subjects design is inconsistent with our aims. Second, we do not expect daily cigarette consumption to change in a group of smokers instructed to continue smoking as usual. Third, utilizing a within-subjects design allows us to maximize statistical power and take advantage of the high within-individual correlation of the primary outcome measure so that we can detect differences in smoking behaviors as participants switch to IQOS.

4.1.2 Rationale for nontreatment-seeking smokers

Consistent with previous studies of IQOS use among cigarette smokers, we will recruit smokers who are not seeking smoking cessation treatment. The goals of this study are to evaluate the effects of IQOS use on cigarette smoking behaviors and to examine which subjective and objective effects of IQOS predict greater IQOS use relative to cigarette smoking. Because the proposed study is not a smoking cessation treatment study, and we are thus not providing treatment, it would be inappropriate to recruit smokers wishing to quit. However, to increase the likelihood that participants will represent smokers likely to use IQOS, eligible smokers will include smokers who would like to quit smoking cigarettes within the next six months, but not within the next 30 days. Smokers reporting a desire to quit in the next 30 days are typically treatment seekers.

4.1.3 Rationale for study duration

We have previously conducted research on the effects of progressively decreasing nicotine levels on cigarette smoking behaviors and subjective effects across 10-day duration periods. Significant decreases in smoking behavior and subjective ratings of cigarette characteristics were observed within this 10-day period. We have also observed significant effects on smoking behaviors in menthol cigarette smokers who switched to a non-menthol brand across a 15-day period, especially between days 10-12. In previous studies, we observed that most daily cigarette change occurs within the first 12 days of product use and then remains unchanged for at least the next 4 weeks. Phillip Morris conducted the only longitudinal study of IQOS use among cigarette smokers under naturalistic conditions. Across six weeks of observation, the majority of change occurred in

CONFIDENTIAL

This material is the property of the University of Pennsylvania. Do not disclose or use except as authorized in writing by the study sponsor

the first weeks of IQOS use, with little to no change thereafter. Given these findings, we expect to detect the majority of change in IQOS use and cigarette smoking across 14 days.

4.1.4 Rationale for providing IQOS, but not smokers' own brand of cigarettes

IQOS will be provided to participants at no cost, but cigarettes will not. This decision is based on methodological, budgetary, and logistical reasons. One, it is not feasible to maintain every variety of cigarette brand that smokers use. Two, we are interested in how IQOS use impacts smoking behavior. By providing cigarettes, we may alter cigarette smoking behavior by implying that we expect participants to smoke their usual brand in addition to IQOS. Three, smokers who purchase IQOS in the natural environment are likely to have a limited supply of cigarettes available, because their intent is to switch to IQOS. As such, not providing a 14-day supply of cigarettes maximizes external validity.

5 CHARACTERISTICS OF THE STUDY POPULATION

5.1 Target Population

Participants will be males and females between the ages of 18-65 who report smoking at least 5 cigarettes/day for at least the past 12 months.

5.2 Accrual

We propose to recruit 160 total participants (40 pilot study participants, 120 full study participants) to complete a 21-day duration protocol over an 8 month period. Their six laboratory visits will occur about every three days. This will allow approximately four to five participants to be recruited every month, accounting for scheduling of visits at about the same time of day (within 1 hour), as there is diurnal variation in smoking behaviors. We will use several, proven strategies to encourage completion of the study, such as providing: (1) each participant with a calendar of their appointments throughout the study; (2) reminder calls the day prior to coming in; (3) incentives for each visit; and (4) a bonus for completion of the entire study such that total compensation equals \$500.

5.3 Inclusion Criteria

1. Able to communicate fluently in English (i.e. speaking, writing, and reading).
2. Male and female smokers who are between 18 and 65 years of age and self-report smoking at least 5 cigarettes (menthol and/or non-menthol) per day for at least the last 12 months.
3. Not currently undergoing smoking cessation treatment or planning to quit smoking within the next 30 days.
4. Report an interest in quitting smoking within the next 6 months.
5. Plan to live in the area for the duration of the study
6. Willing to use study provided IQOS devices and HeatSticks during 2 laboratory visits and throughout study participation.
7. Capable of giving written informed consent, which includes compliance with the requirements and restrictions listed in the combined consent and HIPAA form.

5.4 Exclusion Criteria

Subjects who present and/or self-report with the following criteria will not be eligible to participate in the study:

Smoking Behavior

CONFIDENTIAL

This material is the property of the University of Pennsylvania. Do not disclose or use except as authorized in writing by the study sponsor

1. Regular use of nicotine containing products other than cigarettes (e.g. chewing tobacco, snuff, snus, cigars, e-cigs, etc.). Participants agreeing to abstain from using nicotine containing products other than cigarettes for the duration of study will be considered eligible.
2. Current enrollment or plans to enroll in a smoking cessation program over the duration of the study (i.e. 21 days/3 weeks).
3. Provide a CO breath test reading less than 10 ppm at Intake.

Alcohol and Drug

1. History of substance abuse (other than nicotine dependence) in the past 12 months and/or currently receiving medical treatment for substance abuse. Counseling and support groups (e.g. Alcoholics Anonymous and Narcotics Anonymous) will not be considered medical treatment for the purposes of this protocol.
2. Current alcohol consumption that exceeds 20 standard drinks/week.
3. Breath alcohol reading (BrAC) greater than .000 at Intake.

Medical

1. Women, including all individuals assigned as "female" at birth, who are pregnant, breast feeding, or planning a pregnancy over the duration of the study period.
2. Serious or unstable disease within the past year (e.g. cancer, heart disease). Applicable conditions will be evaluated on a case-by-case basis by the Principal Investigator.

Psychiatric

1. Lifetime history of schizophrenia or psychosis.
2. Lifetime history or current diagnosis of active major depression. Participants who maintain a diagnosis of major depression who have not experienced any major depressive episodes in the past 6 months and are stable on antidepressant medication(s) are eligible to participate.
3. Lifetime history of a suicide attempt.

General Exclusion

1. Past, current, anticipated, or pending enrollment in another research program over the study period that could potentially impact subject safety, study data, and/or the study design as determined by the Principal Investigator.
2. Any medical condition, illness, disorder, adverse event (AE), or concomitant medication that could compromise participant safety or significantly impact study performance as determined by the Principal Investigator. Subjects may be deemed ineligible for any of the aforementioned reasons at any point throughout the study, as well as during the initial telephone screen.
3. Significant non-compliance with protocol and/or study design as determined by the Principal Investigator and/o. Subjects may be deemed ineligible at any point throughout the study.

5.5 Vulnerable Populations

Children, pregnant women, fetuses, neonates, or prisoners are not included in this research study. Educationally or economically disadvantaged persons are included but not solely targeted for recruitment. Because of our recruitment efforts for this study, it is possible that University of Pennsylvania employees and students may be invited to participate. Status of participation in the current study will be independent of the participant's work or school activities.

CONFIDENTIAL

This material is the property of the University of Pennsylvania. Do not disclose or use except as authorized in writing by the study sponsor

5.6 Subject Recruitment

Participants may be recruited from print, traditional, and social media advertisements, referrals, and/or from our database of previous participants who have agreed to be re-contacted for future studies. All advertising materials will be submitted to the UPENN IRB for approval prior to distribution/posting. Interested participants will first complete a telephone screen to assess their initial eligibility. Participants who are initially eligible will be screened against our registration database to confirm that they are not currently participating in another research study at our Center and have not previously reported a condition or circumstance that would make them ineligible for the current study. These participants who remain initially eligible will then be invited to attend an Intake Visit at our Center during which they will be presented with the IRB-approved combined informed consent and HIPAA Form and have their final eligibility confirmed. Initially eligible participants will also have the option to review and sign the combined informed consent and HIPAA Form electronically via REDCap prior to completing the rest of the Intake Visit at our Center.

5.7 Early Withdrawal of Subjects

5.7.1 When and How to Withdraw Subjects

[figure not shown]
Participants are free to withdraw from the study on their own accord at any time. In addition, participants may be withdrawn by the Principal Investigator at any time per the exclusion criteria listed previously. No follow-up data collection is required for participants who withdraw or are deemed ineligible throughout the study.

6. Study-Provided IQOS Device and HeatSticks

6.1 Description

Heat-not-burn (HNB) tobacco products are an emerging nicotine delivery innovation designed to deliver nicotine without the toxins associated with combustion. Powered by a rechargeable battery, HNB devices heat (~662 degrees Fahrenheit) rather than combust (~1,112 degrees Fahrenheit) leaf tobacco to produce a nicotine-containing aerosol for inhalation. In 2019, the Food and Drug Administration (FDA) approved the sale of IQOS, the first HNB tobacco product available in the U.S. [4]. Manufactured by Philip Morris International, IQOS consists of three components: (1) a disposable tobacco stick – HeatSticks or HEETS; (2) a holder that heats the tobacco stick via an electronically charged heating blade; and (3) a charger to recharge the holder after each use. To use IQOS, a tobacco stick is inserted into the heating blade within the holder, the holder is turned on, the heating blade is activated, and then the tobacco stick is heated producing a nicotine-containing aerosol. The tobacco stick is heated for approximately six minutes, allowing up to 14 puffs to be taken, offering smokers the opportunity to self-administer nicotine without combustion. **See Figures 2, 3.**

Figure 2.

6.3 Participant Compliance Monitoring

Participants will be required to keep track of the IQOS device and all the HeatSticks provided to them. Therefore, participants will be instructed to return all used HeatSticks, unused HeatSticks within their original packaging, and empty HeatStick packages to the Center at each lab visit. Research staff will fill in a "Product Accountability Log" with the participants at each visit. Any discrepancy between the products dispensed versus the products returned will be discussed and recorded in the log. All unused study HeatSticks will be collected from participants at all visits. Unused HeatSticks returned by a given participant may be re-distributed to the same participant. At the Day 22 Visit, any remaining unused HeatSticks returned by the participants will be collected by the research staff for destruction.

6.4 Receipt, Storage, Dispensing and Return

6.4.1 Receipt of IQOS and Marlboro HeatSticks

IQOS devices and HeatSticks will be shipped directly to the CIRNA and/or purchased from a commercial vendor. Upon receipt of IQOS devices and HeatSticks to the CIRNA, an inventory will be performed and a product receipt log will be filled out and signed by the person accepting the shipment/delivery. Study staff will verify that the shipment/delivery contains all the items noted in the shipment/delivery inventory. Any damaged or unusable IQOS devices and/or HeatSticks in a given shipment/delivery will be documented in the study files.

6.4.2 Storage

IQOS devices and HeatSticks will be held at room temperature in a double-locked location (e.g., a locked cabinet in a locked room).

6.4.3 IQOS and HeatStick Accountability

A master product accountability log will be maintained throughout the study. All product received, distributed to each unique participant, and destroyed will be documented per standardized product accountability procedures.

6.4.4 Return or Destruction of IQOS and HeatSticks (trial completion)

At the completion of the study, there will be a final reconciliation of IQOS devices and HeatSticks purchased, IQOS devices and HeatSticks dispensed, and IQOS devices and HeatSticks remaining. This reconciliation will be logged on a study completion reconciliation form. Any notable discrepancies will be investigated, documented, and resolved if possible.

CONFIDENTIAL

This material is the property of the University of Pennsylvania. Do not disclose or use except as authorized in writing by the study sponsor

7 Study Procedures

7.1 Telephone Eligibility Screen

Individuals interested in study participation will be screened by a qualified member of the research team to determine initial study eligibility. If the participant meets preliminary eligibility, they will be invited to schedule an Intake Visit at which their final eligibility will be confirmed.

7.2 In-Center Visits

7.2.1 Visit Reminders

Participants will typically receive study visit reminders 24 hours prior to their scheduled study visits via phone call, email, and text message (if applicable).

7.2.2 Intake Visit

During Intake, (Duration: ~1.5 hours) participants will:

1. Either hear an informed consent and HIPAA presentation where all the study procedures and institutional policies will be reviewed OR complete a virtual IRB-approved informed consent and HIPAA presentation via REDCap where all the study procedures and institutional policies will be reviewed prior to coming in to complete the remainder of their Intake Visit. The Principal Investigator will determine whether in-person or electronic consent will be collected based on University COVID-19-related guidelines. The in-person consent procedures will proceed as follows: the combined informed consent and HIPAA form will be read verbatim. All participant questions will be answered as appropriate after which the combined informed consent and HIPAA form will be completed (signed and dated) by both the participant and a qualified member of the research team. The electronic consent process will involve the following procedures:
 - a. The participant will be required to view the entire combined informed consent and HIPAA form on REDCap prior to signing the document. Upon completing their reading of the consent, the participant will be offered the opportunity to indicate if they have any questions and a staff member will call the participant to complete a consent discussion via the telephone. All participant questions will be recorded and answered as appropriate after which the combined informed consent and HIPAA form will be completed (virtually signed and dated) by both the participant and a qualified member of the research team.
 - b. The staff will print a signed copies of this completed record, and provide one copy to the participant and save one copy for our records.
2. Confirm the accuracy of information (i.e. name, address, phone number, email [if applicable], date of birth, age, gender, ethnicity, and race) provided during the initial Telephone Eligibility Screen.
3. Complete a UDS (at least 30ml [two tablespoons] of urine). The UDS will assess the use of any study-prohibited medications/recreational drugs (See Key Exclusionary Criteria; Alcohol and Drug).
4. Participants who test positive for any exclusionary medications or recreational drugs per this protocol will be deemed ineligible.
5. Female participants only: Self-administer a CLIA-waived urine pregnancy test.
6. Female participants are advised that participation of pregnant women in this study is prohibited and that they may withdraw at any time.
7. Have height and weight measured.
8. Perform a BrAC assessment to control for alcohol consumption.
9. Participants with a BrAC greater than 0.000 at Intake Visit will be ineligible.

CONFIDENTIAL

This material is the property of the University of Pennsylvania. Do not disclose or use except as authorized in writing by the study sponsor

10. Perform a CO breath assessment and collect self-report smoking behavior over the past 24 hours to control for prior tobacco exposure.
11. Participants with a CO reading less than 10 ppm will be deemed ineligible.
12. Be asked questions about use of marijuana, other tobacco products (besides cigarettes), or vaping of any substance including tobacco/nicotine or other drugs in the past month.
13. Complete a Medical History Form with a member of the research team to review for applicable contraindications, including psychiatric exclusions, previously listed under Inclusion and Exclusion Criteria (section 4.3 and 4.4).
14. Complete a baseline concomitant medication review (if applicable).
15. Complete questionnaires:
16. Demographics
17. Smoking History (e.g., duration, rate, regular and/or menthol)
18. Nicotine Dependence (FTND)
19. Motivation to quit smoking (Contemplation Ladder)
20. Provide instructions to smoke as usual for the first five days of the study protocol (assessment of baseline smoking rate).
21. Be provided with five date-stamped zipped baggies by the research staff.
22. Review a written instruction card for the collection and storage of used cigarette filters with the research staff.
23. Be instructed to engage in overnight smoking abstinence (10-hours) the night of Day 5 in preparation for the Day 6 Visit.
24. Tentatively schedule study visits with a member of the research team.

7.2.3 Day 6 Visit

During the Day 6 Visit, (Duration: ~1.25 hours) participants will:

1. Arrive at the Center at 9:00 AM after having abstained from smoking overnight.
2. Perform a CO breath assessment and concomitant medication review.
3. Be asked questions about use of marijuana, other tobacco products (besides cigarettes), or vaping of any substance including tobacco/nicotine or other drugs in the past month.
4. Have their overnight smoking abstinence (10-hours) verified by a CO measurement of 50% of Intake visit's CO value
5. Return five date-stamped zipped baggies containing all spent cigarette filters from Days 1-5.
6. Receive instructions on how to use the IQOS prior to two IQOS HeatStick exposures (one regular, one menthol).
7. Be required to use the IQOS device in the lab, where they will be exposed to two IQOS HeatSticks (one regular, one menthol)
 - Participants will take 14 puffs from the regular HeatStick, then take 14 puffs from the menthol HeatStick. These two exposures will be separated by 45 minutes.

[figure not shown]
CONFIDENTIAL

This material is the property of the University of Pennsylvania. Do not disclose or use except as authorized in writing by the study sponsor

8. Complete questionnaires after each exposure:

- Adverse Events Form (Open-Ended AEs)
- Questionnaire of Smoking Withdrawal Symptoms (MNWS)
- IQOS Risk Perceptions
- Subjective Reward of IQOS (CES adapted for IQOS use)

9. Be reminded to engage in overnight smoking abstinence (10-hours) in preparation for the Day 7 Visit.

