4.1 General Design

We propose to conduct a within-subjects study of the impact of IQOS use on smoking behavior among 160 combustible cigarette smokers. Eligible smokers will participate in 8 visits across a 21-day protocol. Participants who are eligible based on telephone screening will complete an in-person Intake Visit (**day 0**). Those eligible will complete measures of demographics, smoking history, and motivation to quit smoking. Baseline cigarette smoking rate will be established during **days 1-5** by instructing participants to smoke as usual for the following five days (**days 1-5**), while collecting their spent cigarette filters each day. Participants will return to the lab on **day 6** after overnight smoking abstinence (CO < 10). Participants will be required to use the IQOS device in the lab, then complete an assessment of IQOS-associated craving relief, withdrawal relief, subjective rewarding value of IQOS, and IQOS-associated risk perceptions. Participants will also return to the Center on **day 7** after overnight smoking abstinence (CO value 50% of Intake visit's CO value) for an assessment of the Relative Reinforcing Value of IQOS (RRVI) after required use of the IQOS device in the lab. **See Figure 1.**

Participants will then be instructed to use IQOS (versus cigarettes) for the following 14 days (**days 8-21**). Participants will collect their used cigarette filters and their used IQOS HeatSticks daily in order to assess consumption of cigarettes per day and sticks per day. Participants will return to the Center on days 11, 14, 17, and 21 to have their carbon monoxide (CO, exhaled breath) measured, and to return their used tobacco sticks and any spent cigarette filters. Cigarette smoking status will be assessed via self-report, spent cigarette filters, and biochemically verified (CO value 50% of Intake visit's CO value). Changes in motivation to quit smoking will be measured at study end, and all remaining used sticks and spent cigarette filters will be returned on Day 22.

On Day 22, participants will be: (1) informed of the lack of data supporting IQOS as a smoking cessation aid or harm reduction tool; (2) cautioned on the likelihood of dual use and the risks

CONFIDENTIAL

This material is the property of the University of Pennsylvania. Do not disclose or use except as authorized in writing by the study sponsor

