7.3 Table 1. Study Measures and Time Points

Table 1. Measures		Bio-behavioral Laboratory Visits							
Description of Time Point		Intake			Days 8-21: Switch to IQOS				End of study
Day #		Day 0	Day 6	Day 7	Day 11	Day 14	Day 17	Day 21	Day 22
Demographic & Baseline Covariates									
Demographics	X								
Smoking History	X								
Nicotine Dependence	X								
Cigarettes per day (days 1-5)		X							
CO	X	X	X	X	X	X	X		
Predictor Variables									
Craving Relief		X							
Withdrawal Relief		X							
Subjective Reward of IQOS		X							
IQOS Risk Perceptions		X							
Relative Reinforcing Value of IQOS			X						
IQOS sticks per day				X	X	X	X	X	
Outcome Variables									
Cigarettes per day				X	X	X	X	X	
Quitting Motivation	X								X

CONFIDENTIAL

This material is the property of the University of Pennsylvania. Do not disclose or use except as authorized in writing by the study sponsor

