7.4.2 Predictor variables

Motivation to Quit Smoking (Contemplation Ladder): The contemplation ladder will be used to assess readiness to consider smoking cessation [59]. The contemplation ladder is designed to measure a smokers position on an 11-point scale (0-10) range, from having no thought of quitting to taking action to quit, and has been successfully employed in several diverse smoking populations [60-62]. We will assess changes in quitting motivation from Intake to Day 22 (end of study).

Craving: Craving will be measured on Day 6 with the well-validated and reliable 10-item brief Questionnaire of Smoking Urges [48-50]. Items are scored from (1=strongly disagree to 7=strongly agree).

Withdrawal symptoms will be measured on Day 6 with the Minnesota Nicotine Withdrawal Scale [51]. This 15-item scale assess withdrawal symptoms with respect to a specific frame of time (0=none to 4=severe).

Subjective rewarding value of IQOS will be measured on Day 6 with the Cigarette Evaluation Scale (CES) adapted for IQOS use [15-18,27]. The CES is an 11 item Likert-format (1=not at all to 7=extremely) self-report instrument with established validity and reliability ($\alpha > .80$) [22,23,32,33,52]. We will focus on the Satisfaction Subscale for the measurement of subjective reward [23].

IQOS Risk perceptions will be measured on Day 6 with 12 items. Four items drawn from prior studies will assess absolute health risk and addictive potential [53-56]. Response options include 1=no risk, 2=low risk, 3=moderate risk, 4= high risk, and 5=very high risk. Eight previously validated tobacco use risk perception items will assess risk relative to combustible cigarettes [57,58]. Instructions are "Compared to your own cigarettes that you usually smoke, IQOS is lower in nicotine, lower in tar, are less addictive, are less likely to cause cancer, have fewer chemicals, are healthier, make tobacco use safer, and help people quit smoking." The Likert-style response options range from 1=definitely untrue to 5=definitely true [57,58].

CONFIDENTIAL

This material is the property of the University of Pennsylvania. Do not disclose or use except as authorized in writing by the study sponsor

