H.1.c. will test whether IQOS use decreases smokers' motivation to quit cigarette smoking. This hypothesis will be examined using mixed models. Predictors will include time (baseline, end of study), and H1c will be tested using the z-score corresponding to the baseline to end of study comparison. Secondarily, we will test cumulative IQOS use as the predictor for change in motivation to quit smoking as measured by the contemplation ladder.

The goal of Aim 2 is to examine which subjective and objective effects of IQOS predict cigarette smoking. **H.2.** will test whether participants who report lower IQOS risk perceptions, greater craving relief, greater withdrawal relief, greater IQOS subjective reward, and have a higher relative reinforcing value of IQOS will smoke fewer cigarettes per day during the 14-day switching period. For H.2., we will remove the daily IQOS counts from the model to avoid confounding, and evaluate the laboratory measures from days 6 and 7 (i.e., IQOS risk perceptions, craving relief, withdrawal relief, subjective reward, and reinforcing value of IQOS relative to cigarettes) for entry in to the model as predictors, using the significance of the corresponding z-score.

8 Risks / Benefits

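### No craving or withdrawal reading is specified before the first Day 6 HeatStick, so run as listed two of the five H2 predictors cannot be derived as relief

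*Combined protocol and SAP*

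**What the plan says.** The H2 analysis in 7.5 tests whether participants with "greater craving relief, greater withdrawal relief", among other characteristics, smoke fewer cigarettes in the switch phase. The other three predictors are risk perceptions, subjective reward and the relative reinforcing value of IQOS. All five come from the Day 6 and Day 7 laboratory visits.

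The sections that should supply the two relief measures are these:

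- **7.4.2** states "Craving will be measured on Day 6 with the well-validated and reliable 10-item brief Questionnaire of Smoking Urges", and it also assigns the MNWS to Day 6. It gives no before or after timing and no change score for either.
- **7.4.1** describes the QSU-B as referring to the present moment.
- **Table 1 (7.3)** has a row for "Craving Relief" and one for withdrawal relief. Each has a single mark, which reads as Day 6.
- **4.1** has participants use the device in the laboratory, "then complete an assessment of IQOS-associated craving relief, withdrawal relief, subjective rewarding value of IQOS".
- **7.2.3** opens the visit with arrival after overnight abstinence and then "Perform a CO breath assessment and concomitant medication review". Product-use questions, the abstinence check, filter return and IQOS instructions follow, and then the two HeatSticks: "These two exposures will be separated by 45 minutes". Only then comes "Complete questionnaires after each exposure", with four forms: adverse events, MNWS, risk perceptions and the adapted CES.

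**The concern.** Relief is the difference between a state before use and a state after it. The QSU-B is an agreement scale and the MNWS a severity scale. Neither asks how much a symptom has been relieved, so a single administration cannot give relief.

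A post-use level mixes how deprived the participant was on arrival with what IQOS then relieved. A heavily deprived participant with large relief and a mildly deprived one with none can leave the same post-use score. H2 would then test whether residual symptoms predict smoking and report the answer as an effect of relief. This is more than a missing scoring rule: a pre-use reading not taken on Day 6 cannot be recovered for that participant at analysis.

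**Working it through.** The plan gives no power or effect figure for H2, so there is none to reproduce. The check is a comparison of sections, followed by an illustration.

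**Comparison of sections**

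| Scale | Assigned to Day 6 in 7.4.2 | Listed before first HeatStick (7.2.3) | Listed after exposure (7.2.3) | Listed at any other visit (7.2.2, 7.2.4 to 7.2.9) |
|---|---|---|---|---|
| QSU-B | yes | 0 | 0 | 0 |
| MNWS | yes | 0 | 2 (one per HeatStick) | 0 |

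1. For withdrawal, two readings are listed and both follow IQOS use. The first cannot stand in for an abstinent baseline, because a HeatStick has already been used.
2. For craving, 7.4.2 and Table 1 plan a Day 6 measure that 7.2.3 does not list. The sections contradict each other. If the QSU-B is given on Day 6 as 7.4.2 says, its timing relative to use is still not stated.
3. 7.5 does not define relief. It says only that the summary scores needed will be created.

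**Illustration of what a post-use score carries**

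Let relief = pre − post, let r be the pre/post correlation and let k = SD(post)/SD(pre). The documents give neither r nor k, so both are assumed. With the sign of the post-use score reversed,

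corr(−post, relief) = (k − r) / √(1 + k² − 2rk), which for k = 1 reduces to √((1 − r)/2).

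| r (k = 1) | Correlation with relief | Shared variance |
|---|---|---|
| 0.3 | √0.35 = 0.59 | 35% |
| 0.5 | √0.25 = 0.50 | 25% |
| 0.7 | √0.15 = 0.39 | 15% |

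The result depends heavily on k. For the same values of r, k = 0.7 gives 0.39, 0.23 and 0.00, and k = 1.3 gives 0.72, 0.68 and 0.64.

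**How relief should be scored once a pre-use reading exists**

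Under the same equal-SD assumption, corr(pre, pre − post) is also √((1 − r)/2), that is 0.59, 0.50 or 0.39. A raw change score therefore still carries the starting level. With the pre-use score in the model as a covariate, entering post or entering pre − post gives the same coefficient with the sign reversed, and the starting level is adjusted for.

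**The case against.** A reader might infer that craving is never collected and relief never measured. The documents do not support that. 7.4.2 assigns the QSU-B to Day 6, 7.4.1 describes it, and 4.1 and Table 1 both plan craving relief. A figure falls within the Day 6 section and Figure 1 is cited in 4.1. Neither is visible here, and either might show timings. 8.3.1 also refers to a Manual of Procedures. What the readable text supports is narrower: no pre-use reading is specified, and the visit list omits a scale that the measures section requires. That still matters, because 11.3.3 relies on checklists at every time point to see that data are collected.

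A second objection is that confounding by dependence is already handled. Table 1 lists nicotine dependence, Days 1-5 cigarettes per day and CO as covariates, and 7.4.1 says CO will be in the models. 7.5 adds demographic and clinical candidates, kept if associated with the outcome at p = 0.2. This stands in part: adjustment would remove some of the starting-level difference. None of these variables records symptoms on the morning of Day 6, so it would not turn a post-use level into relief.

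A third is that the shared-variance figures do not measure harm in this trial. That stands. They rest on assumed correlations and SDs, and the conclusion does not depend on them.

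Finally, H2 could be run on post-use levels. It could, but as a different hypothesis, and the predictors would have to be named accordingly.

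**Conclusion.** The point holds for Aim 2. Following the readable text, craving relief and withdrawal relief, two of the five H2 predictors, cannot be derived as relief. Withdrawal would have post-use levels only. For craving, 7.2.3 must be reconciled with 7.4.2 and Table 1, and even then no pre-use reading is stated. The planned covariates reduce the resulting ambiguity but do not remove it.

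The daily cigarette count and H1a to H1c do not use these measures and are unaffected, so the point should not be read as a threat to the primary result. The shared variance of 15% to 35% is an illustration for r between 0.7 and 0.3 with equal SDs. The conclusion rests on the visit lists, the order of events in 4.1 and the fact that both instruments record levels. It would change only if material not visible here specifies a pre-use administration.

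**What to change.** - **7.2.3:** after the CO abstinence check and before the first HeatStick, add the QSU-B and the MNWS, both with a right-now frame (7.4.2 does not say which time frame the MNWS will use). Add the QSU-B to the forms completed after each exposure.
- **Table 1:** mark craving and withdrawal on Day 6 as pre-exposure and post-exposure.
- **7.5:** define relief from the pre-use and post-use scores, for example as the post-use score adjusted for the pre-use score. State how the scores from the two HeatSticks are combined into one predictor.
- **Flavor order:** 7.2.3 fixes regular then menthol, whereas the data management text in 8.3.1 refers to a counterbalanced order. Reconcile the two, because the way the exposures are combined depends on it.
- **Participants without a pre-use reading:** label the predictor as post-use level, not relief.

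The cost is 10 + 15 = 25 items before exposure and 10 after each of two exposures, so 25 + 20 = 45 extra self-report items in a visit planned at about 1.25 hours. No extra visit is needed. The rest is wording in 7.2.3, Table 1, 7.5 and 8.3.1.
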